Project title:

Effects of combined repetitive transcranial magnetic stimulation and treadmill training on gait performance in Parkinson's disease – a randomised controlled trial

NCT no: NCT02701647

Date of document: 22 Dec 2015

1. Project Title:

Effects of combined repetitive transcranial magnetic stimulation and treadmill training on gait performance in Parkinson's disease – a randomised controlled trial

2. Project Objectives:

There are three objectives in this research study:

1. To compare short- and long-term effects of 25Hz repetitive transcranial magnetic stimulation (rTMS) with 1Hz rTMS followed by treadmill training on their gait performance during single task and dual task conditions in people with Parkinson's disease (PD)
2. To compare short- and long-term effects of 1Hz with 25Hz rTMS followed by treadmill training on corticomotor excitation and intracortical inhibition in people with PD.
3. To explore whether combined rTMS and treadmill training can be transferred to enhancement of balance performance in people with PD

3. Scope and Background of Research:

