Fifty-one participants with PD will be recruited with the following inclusion criteria for study part III: 1) Aged 40 to 70, 2) Diagnosed with idiopathic Parkinson's disease by a neurologist 3) Hoehn & Yahr Scale Stage II to III with stable medications usage 4) ability to walk independently with or without walking aids for 10 metres. The exclusion criteria are as follow: 1) severe comorbidity that may interfere with their ability to participate in the study (e.g. chronic obstructive airway disease, angina, congestive cardiac failure, and significant renal or liver disease, malignancy) 2) significant orthopaedic or rheumatological conditions or disorders of peripheral nervous system that may interfere with mobility or balance performance 3) Female subjects who are pregnant 4) Neurological disease other than PD 5) a score of less than 23 on the Mini-Mental State Examination 6) any auditory or visual impairment 7) History of neurosurgery 8) contraindication to TMS including personal or family history of seizure disorder, metal in the head, implants of medical devices such as cardiac pacemakers or medical pumps (Appendix 1). 9) Subjects with irrepressible tremor and/dyskinesia. Informed consent in accordance with the Declaration of Helsinki will be obtained from all participants and data collection will only be carried out after the approval of Hong Kong Polytechnic University Ethics Committee.

The sample size calculation is based the significant findings of the gait speed and cortical silent period reported by Yang et al. (23). A two-way repeated measures ANOVA design with between-subject group effect (3 levels) and within-subject time effect (4 levels) determines that fifteen subjects per group are required to achieve 85% power to test the interaction effect between group and time effect with a 5% significance level and the effect size is 0.4. By assuming 10% dropout rate, 17 subjects will be required per group.

Experimental protocol

Part I & II. Mapping study and reliability study

Measures of cortical excitability including resting motor threshold (RMT) and recruitment curves will be obtained with transcranial magnetic stimulation (TMS) for 10 healthy subjects for study part I to identify the optimal site for TMS stimulation of the tibialis anterior (TA) muscles.

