Measures of cortical excitability including resting motor threshold (RMT), recruitment curves, intracortical inhibition (SICI) will be obtained with transcranial magnetic stimulation (TMS) for intra-rater and test-retest reliability of all these measures will be established for Study Part II. TMS assessment will be repeated twice, at least 1.5 hour apart within the same session for each study participant to assess the intra-rater reliability. Study participants will be asked to returned 1 week after for TMS assessment to assess the test-retest reliability.

Part III. Interventions

All assessment and treatment will be carried out at the electrophysiology and Gait and balance laboratory. Participants will be randomised into three groups i.e. two experimental groups and a sham group. Participants in the experimental groups will received either 1 Hz or 25Hz real rTMS and control group will receive sham rTMS, followed by treadmill training for 16 sessions over 8 weeks.

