participants will wear a safety harness without body weight support during walking on the treadmill to prevent falls. The maximum tolerated walking speed was determined before training session. Half of the maximum speed will be used for a 5-minute warm up; the training walking speed will be increased by increments of 0.6km/h every 5 minutes. When the belt speed is increased to the highest speed at which the subject could walk safely and without stumbling. This maximum – achieved belt speed will be maintained for 5 minutes and then followed by 0.6km/h decrements. The subject will maintain this speed for the rest of the treadmill session for 15 minutes. If subject is unable to maintain this speed, it will be reduced by 0.6km/h in the next phase. If subject is able to maintain this reduced speed for 5 minutes, the speed will increase during the next phase by 0.6km/h. The treadmill is not included throughout the training. The treadmill training session will last for 30 minutes.

Data Collection

Data will be collected 1 week before intervention and immediately after completion, and at 2 and 6 months after treatment completion. All subjects will be instructed to take their customary medications 1hour before each assessment. The assessor will be blinded to group assignment. During the baseline condition, demographic factors such as age, gender, duration of PD, and the number and daily dosage of anti-parkinsonian medications will be recorded. In each assessment session, the dosage of anti-parkinsonian medications will be recorded.

Outcome measures

Corticomotor excitability

The RMT, RC, CSP duration, SICI of the tibialis anterior muscle elicited by TMS will be used to evaluate motor cortex excitability and inhibition using the procedure described above.

Motor assessment and Functional mobility test

1. Movement Disorders Society-Unified Parkinson's Disease Rating Scale (MDS-UPDRS)

MDS- UPDRS motor scoring will be assessed for each participant a week before the TMS measure. Motor section of the MDS-UPDRS will be used. There are total of 27 items [tremor at rest (arm and leg), action tremor (arm), rigidity (arm and leg), finger taps, hand movements, rapid alternating hand movements, and leg agility]. Each item scores from 0-4, with 0 indicates no disability and 4 maximum disabled.

2. Gait and functional Performance

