All statistical analyses were performed using SPSS version 20.0 software (SPSS Inc., Chicago, IL, USA). Kolmogorov-Smirnov tests will be used to check the normality of data. One-way analysis of variance (ANOVA), Mann-Whitney U tests, and Chi-square tests will be used to compare the dependent variables (demographic data, daily dosage of levodopa, and the number of correct calculated answers/ walking time) among the 1Hz, 25Hz and sham groups. Two-way repeated measures ANOVA will be used to analyze continuous data with measurement interval (baseline, post-treatment, 2-month and 6-month post-treatment) as within-factor and group (1Hz, 25Hz, sham) as between-factor. In the case of an interaction effect between group and time being found, one-way repeated measure ANOVA and *t*-tests with Bonferroni adjustment will be used to determine the real differences. A significance level of 0.05 was employed for analysis.

5. Project Significance and Value:

The progressive and disabling features of PD are the major burden to patients themselves, their families and society as a whole. One of the most disabling motor symptoms is gait difficulty and postural instability. Beneficial long-term effects of rTMS and treadmill training suggest that this intervention could slow down motor function deterioration and maintain gait and balance performance for a relatively long period of time. To be able to walk safely and effectively will promote independence, enhance quality of life, prevent falls and reduced institutionalisation for people with PD.

References:

1. Wu T, Chan P, Hallett M. Effective connectivity of neural network in automatic movements in

Parkinson's disease. *Neuroimage* 2010;49:2581-2587

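### The group-by-time ANOVA treats baseline as an outcome level, names no sphericity correction and leaves its follow-up t-tests undefined: mainly an efficiency loss, fixable in wording

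*Combined protocol and SAP*

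**What the plan says.** Section 4, Statistical analysis: "Two-way repeated measures ANOVA will be used to analyze continuous data with measurement interval (baseline, post-treatment, 2-month and 6-month post-treatment) as within-factor", with the three arms as the between-factor. The follow-up is conditional: "In the case of an interaction effect between group and time being found, one-way repeated measure ANOVA" and t-tests with Bonferroni adjustment are then used. The text does not say whether the t-tests compare arms or visits, or whether they use raw values or changes. The only assumption check named is for normality. No covariate, sphericity test, epsilon correction or multivariate alternative appears anywhere in the document.

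A separate set of between-group tests "will be used to compare the dependent variables (demographic data, daily dosage of levodopa, and the number of correct calculated answers/ walking time") does not depend on the interaction.

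Section 4, Participants, sizes the trial on the same interaction: "fifteen subjects per group are required to achieve 85% power to test the interaction effect between group and time effect", at 5% significance and an effect size of 0.4. It then adds: "By assuming 10% dropout rate, 17 subjects will be required per group". It gives no within-subject correlation, no epsilon and no definition of the effect size.

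The first objective is "To compare short- and long-term effects of 25Hz repetitive transcranial magnetic stimulation (rTMS) with 1Hz rTMS followed by treadmill training on their gait performance". On timing, Part III says the "control group will receive sham rTMS, followed by treadmill training for 16 sessions over 8 weeks", and Data Collection says: "Data will be collected 1 week before intervention and immediately after completion, and at 2 and 6 months after treatment completion". The visits therefore fall at about 0, 2, 4 and 8 months.

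**The concern.** With about 15 evaluable participants per arm, three features of the analysis matter.

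- **Baseline.** As one of four outcome levels, baseline enters the test with a fixed weight and not with the weight its correlation with the outcome supports. The information it carries is only partly used.
- **Sphericity.** The univariate interaction test holds its nominal level only if the visit covariance is spherical. Over eight months correlation may well decay, and nothing is said about a correction.
- **Follow-up tests.** Visit-by-visit comparisons of gait and corticomotor outcomes are reached only through the interaction, and the t-tests are then left undefined. Read as comparisons of visits within an arm, they would not estimate the 25 Hz against 1 Hz difference that the first objective asks for.

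At stake are some power for the test the trial is sized on, a modest excess of false positives, and a defined answer to the first objective.

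**Working it through.** **The plan's own figures.** Dropout reproduces: 15/0.9 = 16.7, so 17 per arm and 3 x 17 = 51. The 85% is not fixed by the stated inputs. If 0.4 is a partial-eta-squared type f, the noncentrality is 0.4² x 42 x 3 = 20.16. With F(6,126) this gives 92.9% power at epsilon 1, and 86.1% at epsilon 0.75. Under another common definition of f, power is at least 98.8%.

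**Assumptions.** The documents give no correlations or effect patterns, so these are assumed: SD 1; visits at months 0, 2, 4 and 8; 15 complete per arm; 25 Hz differs from both other arms. Correlation is either equal (rho 0.5/0.7/0.9) or autoregressive per 2 months (0.3/0.5/0.7/0.9). Simulation error is about 0.3 points for type I error and at most 0.8 for power.

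**One between-arm contrast at one visit, equal correlation.** Variance is proportional to 2(1-rho) for a change score, 1-rho² for a baseline-adjusted value and 1 for a raw value.

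- Change score against adjusted: 2/(1+rho) = 1.33/1.18/1.05.
- Raw value against adjusted: 1/(1-rho²) = 1.33/1.96/5.26.
- Estimating the slope costs a factor 1 + 1/(42-2) = 1.025. The change-score ratios become 1.30/1.15/1.03.

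**Overall test, sustained effect d, equal correlation.**

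- Planned interaction: noncentrality = 15 x d² x (2/3) x (3/4)/(1-rho). For d = 0.5 this is 1.875/(1-rho) = 3.75/6.25/18.75. The equivalent f is the square root of noncentrality/126 = 0.17/0.22/0.39.
- Joint 6-df baseline-adjusted test of arm and arm-by-visit: noncentrality = 15 x d² x (2/3) x 3/[(1-rho)(1+3rho)] = 6.00/8.06/20.27.
- The ratio is 4/(1+3rho) = 1.60/1.29/1.08. At rho 0.9 the 8% advantage is more than offset by estimating an unstructured covariance in a small sample.
- To reach f = 0.4, d must be 0.5 x sqrt(20.16/noncentrality) = 1.16/0.90/0.52 SD.

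Power, with the joint test computed by Wilks' lambda:

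| Case | Planned interaction, uncorrected | Joint baseline-adjusted | Difference (points) |
|---|---|---|---|
| Sustained 0.5 SD, equal 0.5/0.7/0.9 | 24/40/90% | 34/47/88% | +10/+7/-2 |
| Sustained, f = 0.4, equal 0.5/0.7/0.9 | 93/93/93% | 99/96/92% | +6/+3/-1 |
| Sustained 0.5 SD, autoregressive 0.3/0.5/0.7/0.9 | 16/17/25/56% | 36/33/34/70% | +20/+16/+9/+14 |
| Fading 0.5/0.25/0 SD, equal 0.5/0.7/0.9 | 21/38.5/87% | 22/37.5/83% | +1/-1/-4 |

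**Type I error at nominal 5%.**

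- Uncorrected interaction: about 5% under equal correlation. Under autoregressive decay (epsilon 0.95 to 0.68) it runs from about 5% to 7.6%; repeat runs at the strongest decay lay between about 7% and 8%.
- With Greenhouse-Geisser: about 4% to 5%. Its power cost is 1 to 2 points under equal correlation and up to about 10 under decay (56% to 46% at autoregressive 0.9, sustained 0.5 SD).
- Joint 6-df Wald test with Satterthwaite df (6, 41): 5.6% to 6.3%.
- Mixed model with Kenward-Roger df, simulated with 17 per arm and 10% random dropout: 4.7% to 5.4%.

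**The case against.** The strongest reply is that the planned interaction is a valid test of differential change and is the test the trial was sized on. At an f of 0.4 under equal correlation it already has about 93% power, so baseline adjustment gains little. Sphericity inflation is modest, and one sentence naming a correction would remove it. All of this stands. It limits the size of the point but does not supply the correction or define the follow-up tests.

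Some stronger readings are tempting and are not supported:

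- **Baseline as a level biases the comparison.** It does not, under randomisation.
- **The trial has only 24% power.** That figure is for an assumed 0.5 SD at rho 0.5, an f of 0.17, well below the planned 0.4.
- **Unequal spacing itself violates sphericity.** It does not; decaying correlation would.
- **A group main effect averaged over baseline would dilute the treatment effect.** True of that term, but the plan names the interaction as its test and nowhere reads the main effect as the treatment effect.
- **Dropping incomplete rows will bias the result.** Complete-row analysis is inferred from the classical method; the plan states no rule. The allowance covers the numbers lost at 10% (51 x 0.9 = 45.9 against 45), and bias from selective dropout is not shown.

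SPSS can report corrected tests, but the plan does not say which line of output governs.

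**Conclusion.** The concern holds at a moderate level and should be settled before analysis. It has three parts.

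- **Baseline handling is an efficiency matter.** The benefit at the overall test is worthwhile if the effect is sustained and correlation is moderate or decays. It is slight at the planned effect size under equal correlation, and nil or slightly negative at very high correlation or with an effect that fades under equal correlation. For single-visit between-arm contrasts, adjustment never has the larger variance in the cases computed.
- **The missing sphericity correction is a modest validity matter**, and only if the covariance is not spherical.
- **The undefined t-tests need no assumption to establish.** As written, the plan does not fix the comparison that answers the first objective.

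The sizes rest on assumed correlations and effect patterns, and on reading 0.4 as a partial-eta-squared type f. Confidence in the omissions is high; in the sizes it is medium.

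**What to change.** **Preferred.** Analyse the post-treatment, 2-month and 6-month values in a mixed model with arm, visit, arm-by-visit, baseline and baseline-by-visit. Use an unstructured covariance and Kenward-Roger df.

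- Make the joint 6-df test of arm and arm-by-visit the overall test. Arm-by-visit alone must not serve: with baseline no longer a level, it has no power beyond 5% against a constant effect.
- Do not use Satterthwaite df for the 6-df test, because at this size it gives about 6% type I error.
- Then estimate 25 Hz minus 1 Hz, 25 Hz minus sham and 1 Hz minus sham at each visit from the same model with the planned Bonferroni adjustment. State the family: three contrasts at three visits make nine per outcome, so the per-test level is 0.05/9 = 0.0056, against 0.05/3 = 0.0167 if each visit is its own family.

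**Minimum alternative.** Keep the ANOVA, apply the Greenhouse-Geisser correction to the interaction, and specify the between-arm follow-up comparisons as ANCOVA adjusted for baseline.

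**Cost.** Wording only; baseline and every visit are already collected. Another package may be needed for Kenward-Roger df. The preferred model may lose a few points of power at very high correlation or with a fading effect. The minimum alternative gives up the Greenhouse-Geisser power cost shown above.

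### The four-visit repeated measures ANOVA that gates the follow-up tests has no missing-data rule; a mixed model on all available visits is a cheap improvement, at a small power cost that should be stated

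*Combined protocol and SAP*

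**What the plan says.** The only planned analysis of continuous outcomes over time is in section 4, Statistical analysis: "Two-way repeated measures ANOVA will be used to analyze continuous data with measurement interval (baseline, post-treatment, 2-month and 6-month post-treatment" as the within-factor and the three groups as the between-factor. What follows is conditional: "In the case of an interaction effect between group and time being found", one-way repeated measures ANOVA and t-tests "with Bonferroni adjustment will be used to determine the real differences". The software is named ("All statistical analyses were performed using SPSS version 20.0 software"), but no procedure or missing-data option is.

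The sample size paragraph under Participants uses the same design: "A two-way repeated measures ANOVA design with between-subject group effect (3 levels) and within-subject time effect (4 levels"). It states that "fifteen subjects per group are required to achieve 85% power to test the interaction effect between group and time effect". Loss is mentioned only there: "By assuming 10% dropout rate, 17 subjects will be required per group".

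Data Collection sets assessments one week before the intervention, at its end, and 2 and 6 months later. With 8 weeks of training, that is about eight months. Objective 1 covers both horizons: "To compare short- and long-term effects of 25Hz repetitive transcranial magnetic stimulation (rTMS) with 1Hz rTMS followed by treadmill training".

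The document defines no analysis set, does not say whether participants are analysed as randomised, and gives no imputation rule or treatment of a missed visit.

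**The concern.** Classical repeated measures ANOVA needs every participant's value at all four visits, and by default leaves out anyone with a gap. This is a property of the method, not something the plan states. The t-tests could use everyone seen at a given visit, but they are reached only through the interaction test. So the short-term 25 Hz versus 1 Hz comparison in objective 1 passes through a test whose membership depends on attendance at 6 months.

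Two things are at stake. Data already collected on people who leave later are discarded. And if leaving is related to response and the rates differ between arms, the completer comparison can be biased in either direction. A single response-related rule applied to all arms also produces unequal rates when there is a true effect.

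**Working it through.** **1. The plan's own figures.** 15 / (1 - 0.10) = 16.7, so 17 per group and 3 x 17 = 51; this reproduces. After 10% loss, 17 x 0.90 = 15.3 per group remain, against 15 required. The expected number dropped is 51 x 0.10 = 5.1. The 85% power at 15 per group cannot be confirmed, because the effect-size convention, the correlation between visits and the non-sphericity factor are not given. With effect size 0.4 and sphericity, the conventions tried give 92.9% to above 99.9%. One of them gives 84.2% to 86.1% with an assumed non-sphericity factor of 0.70 to 0.75. The figure is not shown to be wrong and is taken as given below.

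**2. Bias at post-treatment.** Assumed: unit variance, correlation 0.7 between all visits, true 25 Hz minus 1 Hz difference in change 0.50 SD, and all loss after the post-treatment visit. The variance of change is 2 x (1 - 0.7) = 0.6, so the standard error of the difference is sqrt(2 x 0.6 / 17) = 0.27 SD. The dropout probability is p = logistic(a + b x change), with b = -1 or -2 and a set to give each arm's rate. The completer mean is E[change x (1 - p)] / E[1 - p]. Ranges are over the two slopes.

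| Loss, 1 Hz vs 25 Hz | Completer estimate (true 0.50) |
|---|---|
| 10% vs 10% | 0.50 |
| 12% vs 8% | 0.46-0.48 |
| 20% vs 5% | 0.37-0.42 |
| 5% vs 20% | 0.58-0.63 |
| one common rule averaging 10% (12% vs 8%, or 14% vs 6%) | 0.44-0.48 |

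The mixed model returns 0.50 in these cases because loss was generated as missing at random. If loss depends on the unseen 6-month change (20% vs 5%), the 6-month estimate is 0.37-0.42 in completers and 0.41-0.44 in the mixed model, so only about a quarter of the bias is removed.

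**3. Precision, by timing of 10% random loss.** In units of 1/n, the variance of an arm's mean change to post-treatment is 0.6 / 0.9 = 0.6667 in completers. With all available data it is (1 - 0.49) / (1 - e) + (1 - 0.7)^2, where e is the fraction lost before the post-treatment visit.

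- e = 0: 0.5100 + 0.09 = 0.6000; ratio of standard errors sqrt(0.6667 / 0.6000) = 1.054.
- e = 0.05: 0.5368 + 0.09 = 0.6268; ratio 1.031.
- e = 0.10: 0.5667 + 0.09 = 0.6567; ratio 1.008.

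So completer standard errors are 5.4%, 3.1% or 0.8% wider. A participant with only a baseline value adds almost nothing. At 6 months the gain is 1.5% to 1.8%, for loss after post-treatment or after 2 months.

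**4. Power of the gate with complete data.** The ANOVA interaction has 6 and 3 x (51 - 3) = 144 df; the unstructured model has about 51 - 3 = 48 denominator df. Assume a sustained 0.80 SD difference in the 25 Hz arm only. The noncentrality is n x (2/3) x (3/4) x 0.80^2 / 0.3, which is 16.0 at n = 15 and 18.1 at n = 17. This gives ANOVA power of 85% and about 89-90%. The corrected unstructured test, by simulation, has about 82% and 87%, a cost of 2 to 3 points. If correlation instead decays by 0.8 per visit, the corrected test has 88% at 17 per arm, against 81% for the Greenhouse-Geisser ANOVA.

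**5. Power with loss.** Random 10% loss after post-treatment gives 86% for both. When 10% loss runs the same way in all arms, the ANOVA is behind under one simulated rule (82-85% vs 86%) and slightly ahead under another (87.5% vs 86.2%, Monte Carlo error 2 to 3 points).

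**The case against.** The strongest reply is that the plan already allows for 10% dropout, that bias near that level is small, and that the remedy has costs. Much of this stands. The inflation does cover power at 10% random loss. At 12% versus 8% the bias is 0.02 to 0.04 SD against a standard error of 0.27, and no section suggests a 20% versus 5% split. The plan gives no timing for its 10%: people who leave during the 8 weeks of training have only a baseline value, and the mixed model then recovers almost nothing. Under compound symmetry the corrected test is somewhat less powerful.

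What does not fall is the gap itself. The inflation adds participants but sets no analysis rule, and it says nothing about selective loss. Nor does it cover loss spread over visits: if each of the three post-baseline visits were missed independently by 10% (an assumption), complete cases would fall to 51 x 0.9^3 = 37, below the planned 45.

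A reader might infer that dropout leaves the trial underpowered, or that the mixed model would gain power. Neither is supported near the planned loss: 15.3 per group meets the stated 15, and the simulated comparison goes either way. A reader might also infer that the gate's type I error is badly inflated. Completer ANOVA rejected 11% to 15% under the null only with 25% loss running in opposite directions by arm, and nothing in the document points to that. The 7.1% seen for the uncorrected ANOVA with decaying correlation is a sphericity matter (4.8% with Greenhouse-Geisser), not a missing-data one.

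**Conclusion.** The concern holds as a cheap improvement, not a fatal flaw. The plan is silent on missing visits and on the analysis set, and its default method would discard observed data from the test that controls all later comparisons. The completer rule is inferred from the method; the document does not state it.

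The size is modest near the planned loss and material only if loss is both response-related and clearly unequal. All the bias figures rest on assumed correlation, effect, dropout rule and timing; none can be read from the document.

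It would be too strong to say that the change frees the short-term comparison from 6-month attendance. The retained 6-df gate still includes the 6-month contrasts. What changes is that a missed 6-month visit no longer removes a participant's earlier data. It would also be too strong to say that the mixed model removes the bias: it does so only if data are missing at random.

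**What to change.** In the Statistical analysis section:

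- **Model.** Replace the two-way ANOVA with a REML linear mixed model: arm, visit and arm-by-visit; baseline as one of the four outcome levels; unstructured covariance, with heterogeneous Toeplitz as the named fallback; Kenward-Roger correction.
- **Analysis set.** State that all available visits of all randomised participants are used, analysed as randomised.
- **Gate.** State that this model's arm-by-visit test at 0.05 takes over the gating role, so no extra test is added.
- **Contrasts.** Replace both the one-way repeated measures ANOVAs and the t-tests with contrasts from the same model: three pairwise arm differences in change from baseline at each of three post-baseline visits, 3 x 3 = 9 per outcome, Bonferroni-adjusted.
- **Sensitivity analyses.** Report the completer ANOVA with Greenhouse-Geisser correction. For gait outcomes, add a multiple-imputation shift: move imputed values towards worse function in one arm at a time, in steps of 0.1 baseline SD, up to 1 SD or until the conclusion changes.

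**Cost.** No extra participants, visits or data are needed, but there are four things to accept:

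- With little or early loss and compound symmetry, the gate loses about 2 to 3 points of power.
- The correction matters. With complete data the null rejection rate is 5.1% with Kenward-Roger, 5.8% with Satterthwaite df and 7.9% or more with an unadjusted chi-square test. If the named package lacks the correction, other software is needed.
- Ten covariance parameters must be fitted. The fit converged in all 24,000 simulated trials checked, but real data may behave less well. Compound symmetry is a poor fallback: it rejected 6.9% under the null with decaying correlation.
- Missing at random is assumed, hence the shift analysis.
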